#### **5.1.2.3 Timing of Post Application Sample Collection**

Microbial samples will be collected at 30 seconds ( $\pm$  5 seconds), 10 minutes ( $\pm$  30 seconds), and 6 hours ( $\pm$  30 minutes) post treatment application for both the abdomen and the groin regions. Post application timing begins upon completion of the treatment material application, including drying time. Microbial samples will be collected using the scrub cup technique.

A skin irritation assessment will be performed prior to collection of the post treatment microbial sample collection (30 seconds, 10 minutes, and 6 hours) and a corresponding rating score for each individual skin condition will be recorded in the subject's CRF. See Appendix 14.11.

If an irritation score of 3 for any individual skin condition at any post treatment observation is assigned, the subject will be discontinued from the study and an adverse event will be recorded. See Section 7.3 (Adverse Events). Following final sample collection, residual study materials will be wiped/cleansed

from the subject's skin using mild soap and/or tap water with a paper towel.

## 5.2 Microbiological Methods

### 5.2.1 Microbial Sample Collection / Scrub Cup Technique

Quantitative cultures (screening baselines, treatment baselines and post treatment application) will be obtained by a modification of the cylinder sampling technique of Williamson-Kligman scrub cup technique. To collect the samples, a sterile scrub cup [REDACTED] will be placed on the site and held firmly to the skin. Sampling solution (SS) ([REDACTED]) will be pipetted into the cup and the skin will be scrubbed in a circular motion with moderate pressure for 1 minute using a sterile rubber policeman. Using a sterile transfer pipette, the SS will be removed and placed in a sterile test tube. An additional [REDACTED] of fresh sampling solution will be pipetted into the cup and the scrub procedure will be repeated. This solution will be pooled with the first solution collected.

### 5.2.2 Sampling Solution (SS)

The SS consists of sterile [75mM phosphate buffer ([REDACTED]) containing [REDACTED] lecithin, [REDACTED] Tween® 80, and [REDACTED] Tamol, [REDACTED] (SS).

### 5.2.3 Bacterial Enumeration Methods

Following sample collection, 10-fold serial dilutions (1 mL sample + 9 mL PBW) will be prepared using Butterfield's phosphate buffered water with neutralizers (PBW). One mL aliquots of appropriate dilutions will be pour-plated in duplicate using trypticase soy agar containing neutralizers (TSA+N). Samples must be plated within 30 minutes of collection. After  $72 \pm 4$  hours of aerobic incubation at  $30 \pm 2$ C, colonies will be counted and viable cells in the original sample will be calculated according to Standard Operating Procedures. After incubation, plates may be refrigerated up to 48 hours prior to counting.

Raw colony counts from each dilution will be recorded on the appropriate CRFs for each subject. The average number of microorganisms recovered (CFU/cm^2) of skin for the screening and treatment day baseline samples will be calculated using the following formula to convert the plate CFU values into CFU/cm^2 of skin:

$$R = \log_{10} \left[ \frac{F \left( \frac{\sum c_i}{n} \right) D}{A} \right]$$

Where:

R = the average CFU count in  $\log_{10}$  scale per  $\text{cm}^2$  of skin.

F = total mL of stripping fluid added to the sampling cylinder ([REDACTED]);

$\sum c_i/n$  = average of the duplicate colony counts for each sample collected

D = Dilution of the plates counted ( $10^0$ ,  $10^1$ ,  $10^2$ ,  $10^3$ ,  $10^4$ , or  $10^5$ )

A = Inside area of the sampling cylinder ([REDACTED] [REDACTED])

Dilution may be reported as dilution factor, which is the base 10 logarithm of the dilution. In that case, the factor of 'D' in the equation above will be replaced with  $10^D$ .

#### 5.2.4 Growth Promotion Control

For each batch of plating medium, TSA+N, fewer than 100 CFU of [REDACTED] will be inoculated in a single plate pour plate. A [REDACTED] aged culture of [REDACTED] will be serially diluted in dilution fluid. The CFU added will be confirmed using duplicate trypticase soy agar (TSA) spread plates. The plates will be incubated for  $72 \pm 4$  hours of aerobic incubation at  $30 \pm 2\text{C}$ .

#### 5.2.5 Neutralizer Validation

The effectiveness of the neutralizer system must be validated prior to the study start date to demonstrate that the antimicrobial is effectively neutralized and there is no effect on the growth of microorganisms. A procedure that will include in-vivo sampling will be combined with an in-vitro evaluation using procedures in accordance with ASTM E1054-08. The procedure is attached as Appendix 14.10. These data must be provided in the final report.

### 5.3 Medication(s)/Treatment(s) Not Permitted

Topical or systemic antimicrobial exposure is not permitted within 14 days prior to the day of Screening Day, and during the study. Restrictions include, but are not limited to antimicrobial soaps, antiperspirants/deodorants, shampoos, lotions, perfumes, after shaves, colognes, and topical or systemic antibiotics.

## 5.4 Subject Compliance

Answers to the inclusion/exclusion questions (Inclusion/Exclusion CRFs) asked at the beginning of the screening and treatment phases will determine compliance to the Subject Instructions (Appendix 14.6) provided to each subject upon study participation. Documentation of the Inclusion/Exclusion criteria shall serve as confirmation of subject compliance with the Subject Instructions.

## 6. Assessment of Efficacy

### 6.1 Efficacy Parameters

The primary measure of antimicrobial efficacy is the reduction of skin flora on the abdominal and groin sites 10 minutes following application of the study treatments relative to the Treatment Day baseline counts.

The reduction will first be calculated as  $\log_{10}$  CFU/cm^2 changes from baseline, then the percentage of successes will be calculated from the  $\log_{10}$  CFU/cm^2 reductions (i.e. percent of subjects meeting required reductions = responder rate). A site is considered a responder for the treatment at 10 minutes if it achieves  $\geq 2.0 \log_{10}$  CFU/cm^2 reduction on the abdomen or  $\geq 3.0 \log_{10}$  CFU/cm^2 reduction on the groin.

Responder status will be calculated separately for the abdomen and groin, for each test substance, for each post-treatment sample time, and for each subject. The individual responses will then be grouped to generate an overall responder rate for each anatomical area, for each test substance, and for each post-treatment sample time. The efficacy goal for active products is to have the lower bound of the 95% confidence interval for the responder rate to be greater than or equal to 70%.

### Secondary Endpoints/Analysis

Responder rates at 30 seconds will be calculated identically to the 10 minute rates. At 6 hours a site is considered a responder if it is below baseline; otherwise, 6-hour responder rates will be calculated identically to the 10-minute responder rates. The secondary efficacy goals are to have the 95% confidence intervals for the responder rates to be greater than or equal to 70%. Log10 CFU reductions from baseline will also be calculated for all post-prep samples.

### Study Validity

For a valid study, the active control must make the same objectives that the test article does and both the test article and the active control should be superior to the inactive control at the primary endpoint. The responder rates for both active and inactive treatments at 6 hours are near 100%. Therefore, comparison of responder rates at 6 hours is unlikely to show any difference. Differences in log10 CFU/cm^2 reductions from baseline will be calculated for 6 hours in order to show that the active treatments are more effective than the inactive control.

## 6.2 Assessment Methods

Efficacy will be assessed by sampling the skin using the cup scrub method described in Section 5.2. See Section 8.0 for analysis methods.

# 7. Assessment of Safety

## 7.1 Safety Parameters

The principal measures of safety will be the recording of skin irritation scores and the incidence of adverse events reported during the study.

## 7.2 Assessment Methods for Skin Irritation

After the washout period, the Investigator or designated sub-investigators trained by the Investigator will assess the subject's skin condition and assign a skin irritation rating score (see Appendix 14.11). A skin irritation score will be recorded at both the screening and treatment phases prior to baseline sample collections and prior to each post treatment application sample collection (30 seconds, 10 minutes, and 6 hours).

A corresponding rating score for each individual skin condition, for each site will be recorded in the subject's CRF. (See Appendix 14.11, which includes the following four independent evaluation categories: Erythema, Edema, Rash, and Dryness).

If an irritation score of 1 or greater for any individual skin condition prior to the baseline sample collection (at either the screening or treatment day phases) is assigned, the subject will be excluded from the study (no study treatment will be applied).

If an irritation score of 3 for any individual skin condition at any observation period is assigned, the subject will be discontinued from the study and an adverse event will be recorded. See Section 7.3 (Adverse Events).

## 7.3 Adverse Events

The Investigator is responsible for identifying adverse events that occur to each subject throughout the study and follow-up period. An adverse event can occur at any time during the conduct of the study. Adverse events will be captured for all subjects from the time of screening baselines are taken until the time of discharge from the study. An adverse event can be identified by the Investigator or reported by the subject.

*Note: The Federal Privacy Rule (HIPAA) specifically permits the use and disclosure of protected health information “without written authorization of the individual” when used for public health activities such as reporting adverse events, tracking FDA-related products, enabling recalls, repairs, replacements, lookbacks, or conducting post-market surveillance [45 CFR 164.512]. This use and disclosure is subject to the minimum necessary standard, i.e. “the minimum necessary to accomplish the intended use, disclosure, or request” [45 CFR 164.502(b)(1)].*

Definitions:

Adverse Event/Experience

An Adverse Event/Experience is any unexpected or undesirable experience occurring to a subject during a study, which may or may not be related to the test article. All adverse event/experiences will be recorded and reported according to the Standard Operating Procedures of the laboratory.

All adverse events, regardless of severity or the causal/effect relationship, will be recorded. The severity of the effect will be noted as “Mild,” “Moderate,” or “Severe” according the following definitions:

Mild	Awareness of signs or symptom, but easily tolerated.
Moderate	Discomfort to a degree as to cause interference with normal daily life activities and /or requiring medication.
Severe	Incapacity with inability to work or do usual daily life activities and requiring medical attention/intervention.

Causal Relations of Adverse Event/Experience

When determining the causal/effect relationship to the test article, the relationship will be described as “None,” “Possible,” “Probable,” or “Definite.” The following definitions will be utilized:

None	No association to the test article. Related to other etiologies such as concomitant medications or conditions or subject’s known clinical state.
Possible	Uncertain association. Other etiologies are also possible.
Probable	Clear-cut association with improvement upon withdrawal of the test article. Not reasonably explained by the subject’s known clinical state
Definite	An adverse event with a clear-cut temporal association with exposure to study materials and cannot reasonably be explained by the subject’s known clinical state. Association with study material is confirmed by laboratory testing if possible.

### Serious Adverse Event/Experience

A Serious Adverse Event/Experience is any adverse experience occurring at any dose that results in any of the following outcomes:

- Death;
- A life-threatening adverse drug experience;
- Inpatient hospitalization or prolongation of existing hospitalization;
- A persistent or significant disability/incapacity;
- Congenital anomaly/birth defect;
- An important medical event that may require medical or surgical intervention to prevent one of the previously listed outcomes.

### Unexpected Adverse Event/Experience

An Unexpected Adverse Event/Experience is any adverse drug event/experience not listed in the current labeling for the test article or the current Investigator's brochure. Where test article labeling or Investigator's brochure is not available, anticipated experiences will be based on the known pharmacological/toxicological properties of the test article or ingredients.

### Recording and Reporting

The Investigator or designee records all adverse events on an Adverse Event Record in the subject's CRF. Documentation includes the AE description, severity, seriousness, date of onset and resolution, relationship to the test article, action taken and outcome.

The Investigator must promptly report all treatment related adverse events to the Sponsor. All serious adverse events must be reported to the Sponsor and to the IRB within 24 hours of the Investigator awareness/notification of the event.

If a subject has no adverse event during the study, the absence of such must be recorded on the CRF.

#### **7.4 Follow-up**

If an adverse event/experience occurs, the subject under the direction of the Investigator (or designee) may be referred to the nearest acute care facility for treatment. Serious or Unexpected Drug Event/Experience will be followed to resolution. Any adverse event will be documented on an Adverse Event Report.

## 8. Statistics

### 8.1 Data Sets Analyzed

The Intent-to-Treat (ITT) Population will consist of all subjects who pass the pre-test period prior to baseline screening and are assigned a subject number for treatment. The ITT population (all randomized subjects) will be used for the safety analysis.

[REDACTED] a Modified Intent-to-Treat (mITT)

Population will be used for analysis and consist of all subjects who have at least one site (left or right for abdominal or inguinal) that passed the treatment day baseline and has CFU results for any other sample time for that site. Body sites will be included in the mITT population if and only if they meet the treatment day baseline criteria. The mITT data set will be evaluated for efficacy.

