#### **3.6.2 Subject Discontinuation and Withdrawal**

The Investigator may discontinue individual subjects from the study at any time. Subjects may voluntarily withdraw from the study at any time without reason or consequence. The subject will be asked to report the reason for withdrawal. The Investigator will provide a written report on the appropriate case report form (CRF) including the date and reason for discontinuance. Subjects who qualify on Screening Day and begin the treatment phase may not be re-entered into the study, regardless of whether or not they completed the study.

Any enrolled subject will be discontinued for the following reasons:

1. A skin irritation rating of 3 for any individual skin condition at any evaluation following the application of study treatment. (A skin irritation rating of 2 for any individual skin condition at any evaluation following the application of study material may also be the cause for subject discontinuation at the discretion of the Investigator.)
2. Experiencing a serious protocol deviation that compromises the data results, for example, using a topical antibiotic at a test site during the study.

See section 8.5 for handling of withdrawn subject data.

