#### **4. Subject Selection**

Healthy volunteers with no dermatological conditions or known history of sensitivity to natural rubber latex, adhesive skin products (e.g., Band-Aids, medical tapes), isopropyl alcohol, citric acid, methylene blue, methylparaben, propylparaben, or chlorhexidine gluconate will be enrolled into this study. A sufficient number of volunteers will be enrolled in the screening phase such that the total number of abdominal regions and the total number of groin regions meets or exceeds the number determined for the study (320 abdominal regions and 320 groin regions for the test article and reference article; and 64 abdominal regions and 64 groin regions for the negative control). Subjects must satisfy all Screening Day and Treatment Day Inclusion/Exclusion Criteria prior to screening sample collection and Treatment Day procedures. Volunteers will be recruited and treated in blocks until the count of results in the mITT population meets or exceeds the required test material/region counts.

A subject must qualify for both the abdominal portion and the groin portion of the study. The right and left sides of the abdomen and groin must meet the minimum baseline values stated in the Inclusion Criteria.

Subjects who are treated but discovered to have Treatment Day baseline counts below the minimum values or above the maximum values stated in Table 3.2 will not be included in the primary efficacy analysis based on the body site(s) that did not qualify due to not meeting the treatment day baseline inclusion criteria - see section 4.1.

Subjects will be identified at screening by their initials and a screening ID number. Subject numbers will not be assigned until a subject has passed the screening criteria, including baseline bacterial counts.

All volunteers will be given verbal and written information about the study procedures, and Subject Instructions (Appendix 14.6) will be provided to each subject for the pretreatment

phase of the study. The following Inclusion/Exclusion Criteria will be reviewed on Screening Day and on Treatment Day to establish eligibility for participation:

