#### **8.5 Procedures for Accounting for Missing Data and Protocol Deviations**

Missing microbiological data at 30 seconds, 10 minutes, or 6 hours will be reported as missing; if the entire sample is missing the site will be treated as a nonresponder for that sample time. These subjects will be included in the mITT data set based on the criteria defined above. Details of any other missing data handling will be specified in the statistical analysis.

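### Section 8.1 is inconsistent on whether a treated, baseline-qualified subject with no post-application count belongs in the primary analysis set or drops out of it

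*Combined protocol and SAP*

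**What the plan says.** Four parts of the protocol bear on who is in the primary denominator.

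- **Subject rule, section 8.1.** A subject enters the mITT set through at least one site that "passed the treatment day baseline and has CFU results for any other sample time for that site". A post-application result is therefore a condition of entry.
- **Site rule, section 8.1, next sentence.** "Body sites will be included in the mITT population if and only if they meet the treatment day baseline criteria". This has no post-application condition. The section then states: "The mITT data set will be evaluated for efficacy".
- **Missing data, section 8.5.** For a missing post-application sample, "if the entire sample is missing the site will be treated as a nonresponder for that sample time". It continues: "These subjects will be included in the mITT data set based on the criteria defined above". Section 3.6.2 sends withdrawn subjects here: "See section 8.5 for handling of withdrawn subject data".
- **Recruitment, section 4.** Volunteers are "recruited and treated in blocks until the count of results in the mITT population meets or exceeds the required test material/region counts".

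The primary goal (section 3.2) is a lower 95% confidence bound of at least 70% for the 10-minute responder rate, separately for abdomen and groin. Section 8.2.1 specifies exact intervals.

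**The concern.** The two sentences of 8.1 give different sets for one kind of subject: treated, with a qualifying baseline, and with no count afterwards at any qualified site. Under the subject rule this person is out. Under the site rule the sites are in, and 8.5 makes them nonresponders. Two programmers could build different primary denominators from the same text.

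The subject rule excludes on something that happens after treatment, and the documents show how it could occur. Section 5.1.2.3 says: "A skin irritation assessment will be performed prior to collection of the post treatment microbial sample collection". That covers the 30-second sample, and a score of 3 means discontinuation. Section 3.6.2 also allows discontinuation at a score of 2, at the investigator's discretion. Under section 3.3 the staff who apply product and collect samples know the assignment. Because section 4 recruits to the mITT count, a subject who drops out of the set is made up by another who has data. The test is a single proportion against 70%, so taking a would-be nonresponder out of the denominator can only help the product to pass.

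**Working it through.** **1. Does 8.5 bring the subject back?** Section 3.6.2 refers withdrawn subjects to 8.5, 8.5 refers inclusion back to 8.1, and the 8.1 subject rule needs a post-application count. On that chain the subject stays out. On the 8.1 site rule the subject's qualified sites are in. Amendment 3, which rewords section 4, also gives only a failed Treatment Day baseline as the reason to leave a site out. The text does not settle the matter.

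**2. Who is affected?** A fully evaluable subject has 4 sites and 3 post-application times, so 12 results (section 8.2.1). One count at one qualified site is enough for the subject rule. Only a subject with no count at every qualified site and time is lost. Since each subject carries two products on both regions, one such loss can remove one abdomen and one groin site from each of those two products.

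**3. The plan's own sample size.** Inputs from section 8.3 are 77.8% expected, 80% power and a stated 267; the 70% threshold is from section 3.2. I assume a two-sided 95% interval. The normal approximation is n = [(1.96√(0.70·0.30) + 0.842√(0.778·0.222)) / 0.078]² = 256, or 269 with continuity correction. By the exact rule, 267 sites need at least 202 responders and have 82.1% power. The stated 267 is therefore adequate for 80% power, and 320 is the number planned.

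**4. Pass rule at 320.** With x responders among n, the Clopper-Pearson lower bound is the 2.5% quantile of Beta(x, n − x + 1). For 240/320 it is 69.88% (fail) and for 241/320 it is 70.21% (pass). The rule is at least 241 responders, with a 2.1% chance of passing at a true rate of 70% and 87.2% power at 77.8%.

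**5. Adding back m lost sites as nonresponders.** Section 4 recruits until the mITT count is met, so the comparison is x/320 against x/(320 + m).

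| Observed | Rate | Lower bound | Smallest m that reverses the pass | Lower bound at that m |
|---|---|---|---|---|
| 241/320 | 75.3% | 70.21% | 1 | 241/321: 69.97% |
| 243/320 | 75.9% | – | 4 | 243/324: 69.92% |
| 245/320 | 76.6% | – | 7 | 245/327: 69.86% |
| 249/320 | 77.8% | 72.86% | 12 | 249/332: 69.98% |
| 256/320 | 80.0% | 75.19% | 22 | 256/342: 69.91% |
| 272/320 | 85.0% | 80.61% | 44 | 272/364: 69.93% |

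At 249/320, 11 losses still pass (249/331: 70.21%).

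**6. False-pass chance if the sites are dropped.** Suppose the true rate with missing counted as failure is exactly 70%. Among the 320 observed sites the rate is then 0.70 × (320 + m)/320. The chance of 241 or more responders is 2.5% for m = 1, 3.7% for m = 3, 5.3% for m = 5 and 11.7% for m = 10. The documents give no dropout rate, so m is an assumption throughout.

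**The case against.** The strongest reply is that the gap is very small and partly closed already. The site rule points the right way, and subjects with some data stay in, with their missing samples scored as failures. The first sample is due 30 seconds after drying. The irritation route needs a discontinuation before any sample is taken, in people already screened for known sensitivities, skin allergies and any pre-treatment irritation. All of this stands, and it limits the expected number of such subjects. It does not remove the conflict, because 8.5 makes inclusion depend on the 8.1 criteria.

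A reader might also infer that the worst efficacy outcomes leave the denominator. The documents do not support that. A site with poor kill has a high count and stays in as a failure. The lost subjects have unknown efficacy and are nonresponders only by the 8.5 convention. Severe irritation is a safety outcome, which is analysed in the ITT set, and nothing in the documents ties it to a low log reduction. Nor does a loss fall only on the product that irritated: discontinuation is by subject, so both of that subject's products lose a reading.

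A reader might compare 240/320 with a smaller denominator such as 240/319. A final count of 319 falls short of the recruitment rule in section 4, so the comparison has to add failures to at least 320.

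Part of the mITT sentence is blacked out, so any stated basis for the definition cannot be seen. The operative conditions remain legible.

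**Conclusion.** The point holds as an inconsistency in the definition of the primary analysis set. It affects only treated subjects with a qualifying baseline and no count at any qualified site. It should be corrected, because the literal subject rule is a post-treatment exclusion at odds with the plan's own missing-data rule.

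Its practical weight is probably low. A single loss matters only when the result sits exactly on the boundary, and at the planned rate about 3.6% of sites (12 of 332) would have to be lost in one product and region. It would be too strong to say that the responder rate is inflated: that depends on such a subject existing, and the documents do not say whether one did.

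The figures assume two-sided 95% Clopper-Pearson intervals, exactly 320 observed sites per product and region, and every lost site scored as a nonresponder.

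**What to change.** In section 8.1, define the mITT set as every treated site whose Treatment Day baseline meets Table 3.2, and delete the requirement for a post-application CFU result. Section 8.5 then scores a missing 10-minute sample as nonresponse, and its reference back to 8.1 no longer conflicts. Report the number of treated sites with no counts, by product and body region.

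Amendment 6 records that testing was complete when it was issued, so this is now a change after data collection. Describe and justify it in the final report under section 8.6. If any such subject exists, show the primary result under both definitions; if none exists, say so, and the result is unchanged.

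The cost is one clause and one reported count per product and region. The responder rate may become slightly less favourable. With 320 observed sites and a 77.8% rate among them, power falls from 87.2% with no lost site to 84.2% with one (242 responders needed), 80.8% with three (243) and 77.0% with five (244).
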